2.2.2 Dose Rationale

The recommended target dose and schedule is 1500 mg/m², administered Q2W. This is based on consideration of both clinical and non-clinical efficacy and safety data.

With respect to efficacy, ASP1650 significantly inhibited tumor growth in a mouse testicular cancer xenograft model and prolonged survival over a dose of 4.375 mg/kg to 35 mg/kg three times a week (3xW) corresponding to estimated ASP1650 trough concentrations of 12.5 μ g/mL to 100 μ g/mL. Animals treated with 17.5 mg/kg (90.77%) or 35 mg/kg 3xW showed > 90% tumor growth inhibition (90.88%) with prolonged survival. The respective ASP1650 trough concentrations were estimated to be 50 and 100 μ g/mL.

With respect to safety, no ASP1650-related toxicities were noted in either single dose study in cynomolgus monkeys or 28-day weekly intravenous dose study in mice (100 mg/kg). The MTD was not achieved in the 1650-CL-0101 study, as none of the AEs were considered dose limiting. Elevated amylase was reported in 3 subjects in the ovarian study, with 1 each in 100, 300 and 1000 mg/m² dose group. However, exposure safety analysis did not reveal any relationship between drug exposure and amylase values.

Using human pharmacokinetic data from the 1650-CL-0101 study, modeling and simulation results support a dosing schedule of 1500 mg/m² Q2W instead of the every 3 weeks (Q3W) schedule employed in the 1650-CL-0101 study. A dosing schedule of 1500 mg/m² Q2W is anticipated to lead to a mean trough concentration of 144 µg/mL with approximately 80 and 60% of subjects having trough values above 50 and 100 µg/mL, respectively.

A starting dose of 1000 mg/m² Q2W is recommended in this study, which represents a 30% higher dose intensity compared to 1000 mg/m² Q3W in the OVAR study. If no dose limiting toxicities are observed in 1000 mg/m² Q2W dose, the dose will be increased to 1500 mg/m² Q2W. This represents a 31% increase in C_{max}.

2.3 Randomization

N/A

3 SAMPLE SIZE

The sample size for the Safety Lead-in phase is not based on a statistical power calculation. The planned number of up to 18 subjects would provide adequate information for the objectives of the safety cohort.

Simon's optimal 2-stage design [Simon, 1989] will be used for conducting phase 2 of the study. The null hypothesis is that the true ORR is 10%, and the alternative hypothesis is that the true ORR is 25%. The study will be carried out in 2 stages. In stage I, a total number of 13 subjects treated at the RP2D will be evaluated.

If there is 1 or fewer responses among these 13 subjects, the study will be stopped early for futility. Otherwise, an additional 21 subjects will be enrolled in stage II, resulting in a total number sample size of 34. If there are 6 or more responses among these 34 subjects, we reject the null hypothesis and claim that the treatment is promising. The design controls the type I error rate at 10% and yields the power of 80%.

4 ANALYSIS SETS

In accordance with International Conference on Harmonization (ICH) recommendations in guidelines E3 and E9, the following analysis sets will be used for the analyses.

Detailed criteria for analysis sets will be laid out in classification specifications and the allocation of subjects to analysis sets will be determined prior to database hard-lock.

4.1 Full Analysis Set

The full analysis set (FAS) will consist of all enrolled subjects. This will be the primary analysis set for efficacy analyses.

4.2 Safety Analysis Set

The safety analysis set (SAF) consists of all subjects who took at least 1 dose of study drug, and will be used for safety analyses.

For the statistical summary of the safety data, the SAF will be used.

4.3 Pharmacokinetics Analysis Set

The pharmacokinetic analysis set (PKAS) will consist of the subset of the SAF for which at least 1 ASP1650 concentration measurement is available. Additional subjects may be excluded from the PKAS at the discretion of the pharmacokineticist. The PKAS will be used for description of pharmacokinetic data.

4.4 Dose Limiting Toxicity Evaluation Analysis Set (DEAS)

The dose limiting toxicity evaluation analysis set (DEAS) is defined as all subjects in SAF by excluding the subjects who meet the following criterion:

- A subject without a DLT who receives less than the planned ASP1650 dose during the DLT observation period.

DEAS will be used for the analysis of DLT data.

5 EFFICACY AND SAFETY ENDPOINTS

5.1 Primary Efficacy Endpoints

5.1.1 Objective Response Rate

ORR is defined as the proportion of subjects who have a best overall response of confirmed CR or confirmed PR, as assessed by modified RECIST 1.1. A response of CR or PR must be maintained for at least 4 weeks to be confirmed.

For subjects with measurable disease at baseline, the following criteria in [Table 1](#) will be used to assess response using modified RECIST 1.1:

Table 1 Response Criteria Based on Modified RECIST v1.1

Serum Markers	Target Lesions	Non-Target Lesions	New Lesions	Overall Timepoint Response Assessment	
	(target lesion response)	(non-target lesion response)	(unequivocal new lesions)		
Values that fall below the ULN for the assay employed	CR	CR	No or Equivocal	CR	
	CR	Not Applicable	No or Equivocal	CR	
	Not applicable	CR	No or Equivocal	CR	
For both AFP and beta-hCG, no increase \geq 50% in 2 samples at least 1 week apart compared to nadir values, at least one of the values are above ULN	CR	CR	No or Equivocal	PR	
	CR	Not Applicable	No or Equivocal	PR	
	Not applicable	CR	No or Equivocal	PR	
For both AFP and beta-hCG, no increase \geq 50% in 2 samples at least 1 week apart compared to nadir values	CR	Non-CR/Non-PD	No or Equivocal	PR	
	CR	NE/ND	No or Equivocal	PR	
	PR	CR	} = not PD	No or Equivocal	PR
	PR	Non-CR/Non-PD		No or Equivocal	PR
	PR	NE/ND	No or Equivocal	PR	
	PR	Not applicable	No or Equivocal	PR	
For both AFP and beta-hCG, no increase \geq 50% in 2 samples at least 1 week apart compared to nadir values	SD	CR	} = not PD	No or Equivocal	SD
	SD	Non-CR/Non-PD		No or Equivocal	SD
	SD	NE/ND		No or Equivocal	SD
	SD	Not applicable		No or Equivocal	SD
Any	PD	Any	Any	PD	
Any	Any	PD	Any	PD	
Any	Any	Any	Yes or Unequivocal	PD	
Increase \geq 50% in serum tumor markers AFP or beta-hCG in 2 samples at least 1 week apart compared to nadir values	Any	Any	Any	PD	
NE/ND	NE/ND	Not PD	No or Equivocal	NE	

CR: complete response; ND: not done; NE: non-evaluable; PD: progressive disease; PR: partial response; SD: stable disease.

Confirmatory assessment for CR or PR should be done at least 4 weeks after the date of the CR or PR was first observed.

In subjects whose only evidence of disease is elevated serum tumor markers ($> 2 \times$ ULN AFP or $> 2 \times$ ULN β hCG) at baseline, the modified RECIST v1.1 will reduce to serum tumor marker response criteria. Serum marker criteria can be found in section 5.3.1.3 of the protocol. In subjects whose only evidence of disease is elevated serum tumor markers ($> 2 \times$ ULN AFP or $> 2 \times$ ULN β hCG) at baseline, confirmatory assessment for CR or PR is not required.

Best overall response is determined once all tumor response data for the subject is available. Subjects will be classified by best response on study as outlined in modified RECIST v1.1 criteria. For best overall response of stable disease (SD), SD must be documented as present at least once after study entry and maintained for at least 12 weeks.

ORR as assessed by RECIST 1.1 alone and by serum marker alone will be performed as a sensitivity analysis.

5.2 Secondary Efficacy Endpoints

5.2.1 Clinical benefit rate (CBR)

CBR is defined as the proportion of subjects for each dose level whose best overall response is rated as confirmed CR, PR or durable SD, as assessed by modified RECIST 1.1. Durable SD is a SD maintained for at least 12 weeks.

CBR will be assessed for subjects, using RECIST 1.1 alone, and using serum markers alone.

5.2.2 Duration of Response

Duration of Response (DOR) will be calculated only for the subgroup with confirmed response CR/PR.

DOR is defined as the time from the date of the first confirmed response CR/PR (whichever is first recorded) as assessed by modified RECIST 1.1 to the date of disease progression (assessed by modified RECIST 1.1) or date of censoring, whichever is earlier. If a subject has not progressed, the subject will be censored at the date of last disease assessment or at the date of first confirmed CR/PR if no post-baseline disease assessment is available. DOR will be derived for subjects with best overall response as confirmed CR or confirmed PR.

DOR (in days) is calculated as:

(Date of documented PD, death, or censoring) – (Date of the first CR/PR which is subsequently confirmed) +1.

To apply the cut-off date to DOR is to exclude disease assessments after cut-off date in the analysis.

DOR will be calculated for each subject using RECIST 1.1 alone, and serum markers alone.

Table 2 DOR Definition

Situation	Date of Event or Censor	Outcome
Subject with confirmed CR/PR:		
Disease progression documented per modified RECIST v1.1	Date of PD	Event
No disease progression	Date of last efficacy assessment or at the date of first CR or PR if no postbaseline efficacy assessment is available	Censor

DOR = Date of Event or Censor – Date of first CR or PR +1

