5.2.3 Progression-Free Survival (PFS)

PFS is defined as the time from the date of first dose until the date of disease progression as assessed by modified RECIST 1.1, or until death due to any cause. If a subject has neither progressed nor died, the subject will be censored at the date of last disease assessment or at the date of registration if no post-baseline radiological assessment is available. Subjects who receive any further anticancer therapy for the disease before disease progression will be censored at the date of the last disease assessment before the anticancer therapy started. If progression or death occurs after missing 2 scheduled disease assessments, the subject will be censored at the date of last disease assessment or at the date of registration if no post-baseline disease assessment is available. A subject has missed 2 scheduled disease assessments if the gap between two disease assessments is more than 2.5 times the scheduled disease assessment interval. During treatment, this will be 105 days (2.5 x 42 days during treatment for the first 24 weeks); during the follow-up period this will be 210 days (2.5 x 84 days during follow-up).

PFS (in days) is calculated as:

(Date of death, or Progression assessed by modified RECIST 1.1, or censoring) – (Date of first dose) +1.

To apply the cut-off date to PFS is to exclude disease assessments, death and anti-cancer therapy date after cut-off date in the analysis.

Note: Patient cannot be censored at “Not Evaluable (NE)”. If NE is the only previous assessment, then PFS will be censored at Day 1.

PFS will be calculated for each subject using RECIST 1.1 alone, and serum markers alone.

Table 3 PFS Definition

Situation	Date of Event or Censor	Outcome
No evaluable post-baseline efficacy assessments, no death	Date of first dose	Censor
Subject did not receive new anti-cancer therapy:		
Disease progression documented per modified RECIST v1.1	Date of PD	Event
No disease progression, but death recorded on eCRF	Date of death	Event
No PD nor death	Date of last efficacy assessment or at the date of first dose if no postbaseline efficacy assessment is available	Censor
Subject received new anti-cancer (ACT) therapy:		
Disease progression documented per modified RECIST v1.1 after new ACT	Date of last efficacy assessment before start of new anti-cancer therapy or at the date of first dose if no post-baseline efficacy assessment is available	Censor

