6.11 Additional Conventions

6.11.1 Missing Data

Every effort will be made to resolve missing or incomplete dates for adverse events, concomitant medications, anti-cancer therapy, and death. If a partial date cannot be resolved, the most conservative imputation methods will be used to complete the missing information.

Missing or partial start and stop dates of adverse events and concomitant medication will be imputed using the following algorithm:

- Imputation rules for partial or missing stop dates:
 - If the month and year are present, then impute as the last day of that month.
 - If only the year is present, impute as December 31 of that year.
 - If the stop date is entirely missing, assume the event or medication is ongoing.

Imputation rules for partial or missing start dates:

Start Date		Stop Date				Partial: yyyy		Missing
		Complete: yyyymmdd		Partial: yyyymm		< 1 st dose	≥ 1 st dose	
		< 1 st dose	≥ 1 st dose	< 1 st dose yyyymm	≥ 1 st dose yyyymm	< 1 st dose yyyy	≥ 1 st dose yyyy	
Partial: yyyymm	= 1 st dose yyyymm	2	1	2	1	n/a	1	1
	≠ 1 st dose yyyymm		2		2	2	2	2
Partial: yyyy	= 1 st dose yyyy	3	1	3	1	n/a	1	1
	≠ 1 st dose yyyy		3		3	3	3	3
Missing		4	1	4	1	4	1	1

1 = Impute as the date of first dose; 2 = Impute as the first of the month; 3 = Impute as January 1 of the year; 4 = Impute as January 1 of the stop year

The imputed dates will be used to determine whether an AE is/is not treatment emergent. Listings of AEs and concomitant medications will present the actual partial dates; imputed dates will not be shown.

For secondary endpoint PFS or DOR, missing or incomplete death date will be imputed as the earliest feasible date on or after the date last known to be alive as the examples shown in the table below.

Incomplete Date of Death (YYYY MMM DD)	Date Last Know to be Alive (YYYY MMM DD)	Imputed Date of Death (YYYY MMM DD)
2005 APR ??	2005 MAR 31	2005 APR 01
2005 ??? 13	2005 MAR 31	2005 APR 13
2005 ??? ??	2005 MAR 31	2005 MAR 31
???? APR ??	2005 MAR 31	2005 APR 01
???? APR 13	2005 MAR 31	2005 APR 13
???? ??? ??	2005 MAR 31	2005 MAR 31

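### SAP 5.2.2 contradicts itself on whether a confirmed responder who dies without progression counts as an event or is censored in duration of response

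*SAP*

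**What the plan says.** SAP 5.2.2 addresses the end of DOR in several places, and they do not agree.

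- **Narrative.** DOR runs from first confirmed response to progression or censoring. It adds: "If a subject has not progressed, the subject will be censored at the date of last disease assessment". Death is not mentioned.
- **Formula.** The end date is "Date of documented PD, death, or censoring". Death is listed separately from both progression and censoring, but is not labelled as either outcome.
- **Table 2.** It has two rows. Documented progression is an Event. No progression is a Censor, dated "Date of last efficacy assessment or at the date of first CR or PR if no postbaseline efficacy assessment is available". The footer is "DOR = Date of Event or Censor – Date of first CR or PR +1".
- **Cut-off sentence.** "To apply the cut-off date to DOR is to exclude disease assessments after cut-off date in the analysis". Death is not named.
- **Other versions.** "DOR will be calculated for each subject using RECIST 1.1 alone, and serum markers alone". Neither has an event rule of its own.

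SAP 6.11.1 then says: "For secondary endpoint PFS or DOR, missing or incomplete death date will be imputed as the earliest feasible date".

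PFS in SAP 5.2.3 is explicit by contrast. Its censoring sentence covers subjects who have neither progressed nor died, its cut-off sentence names death, and Table 3 has a row "No disease progression, but death recorded on eCRF" scored as an Event. Protocol 7.4.2.2 and SAP 6.4.2.2 specify Kaplan-Meier estimation in confirmed responders and do not say how death is handled.

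**The concern.** Two programmers could follow 5.2.2 faithfully and produce different DOR curves. One would use Table 2 and censor a responder who dies without progression at the last assessment. The other would use the formula and end that responder's DOR at death. These are different estimands: time to progression among responders with death treated as uninformative censoring, and time to progression or death.

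The first assumes that a responder who died would otherwise have had the same future risk of progression as those still being followed. That is hard to defend in advanced, refractory disease. In an open-label, single-arm trial, the choice should also not be left until responders' outcomes are known.

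The ambiguity applies to all three DOR versions: modified RECIST, RECIST alone and serum markers alone.

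**Working it through.** **1. Text comparison for a confirmed responder who dies without documented progression**

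| Place | Literal reading |
|---|---|
| 5.2.2 narrative | Censor at last assessment |
| Table 2 and footer | Censor (progression is the only Event row) |
| 5.2.2 cut-off sentence | Fits a progression-only rule |
| 5.2.2 formula | Death is an end date apart from censoring |
| 6.11.1 | Death date is needed for DOR |
| Protocol 7.4.2.2, SAP 6.4.2.2 | Silent |

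The first three fit one rule and the next two fit another. Nothing ranks one above the other.

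**2. How many responders there may be**

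The documents give no DOR figure to reproduce. The design figures come from SAP 3: 13 subjects in stage I, stop at 1 or fewer responses, 21 more in stage II, success at 6 or more of 34.

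With X1 ~ Bin(13, p) and X2 ~ Bin(21, p), P(X1 ≥ 2 and X1 + X2 ≥ 6) is 0.0957 at p = 0.10 and 0.811 at p = 0.25. These agree with the stated 10% and 80%.

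The probability of stopping at stage I is P(X1 ≤ 1):
- p = 0.10: 0.9^13 + 13 × 0.1 × 0.9^12 = 0.254 + 0.367 = 0.621
- p = 0.25: 0.75^13 + 13 × 0.25 × 0.75^12 = 0.024 + 0.103 = 0.127

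Expected responders if stage II opens are [13p − P(X1 = 1)] / P(X1 ≥ 2) + 21p:
- p = 0.10: (1.3 − 0.367)/0.379 + 2.1 = 4.56
- p = 0.25: (3.25 − 0.103)/0.873 + 5.25 = 8.85

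**3. What one death can do to the curve**

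Take 6 responders, the minimum for success, all with an end date, no ties, and one of them dying without progression. This pattern is an assumption for illustration. Compare the Kaplan-Meier value at the third end date.

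When the death is among the first three end dates, progression-or-death gives 5/6 × 4/5 × 3/4 = 0.50. Table 2 gives, for example:
- death first: 4/5 × 3/4 = 0.60
- death second, last scan after the first progression: 5/6 × 3/4 = 0.625
- death third, last scan after the second progression: 5/6 × 4/5 = 0.667

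Table 2 is higher by 0.10 to 0.17.

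Now let the first three end dates be progressions and the fourth be the death, with that subject's last scan between the second and third progressions. Progression-or-death again gives 0.50. Table 2 gives 5/6 × 4/5 × 2/3 = 0.444, which is lower, because the subject has left the risk set before the third progression. Such a gap is plausible with scans 6 or 12 weeks apart.

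**4. Direction**

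If censoring took place exactly at death and samples were large, the progression-only curve could not fall below the progression-or-death curve, because the death hazard is removed. Censoring at the earlier scan also removes time at risk, so a small sample can go the other way.

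**The case against.** The narrative and Table 2 never mention death, so the censoring is inferred from a literal reading. Someone could say that the formula shows the intent, or alternatively that progression-only was intended and that DOR appears in 6.11.1 only because it shares a sentence with PFS. Either is possible, but they point in opposite directions and each leaves some SAP text wrong. The edit is needed whichever was meant.

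The objection on importance largely stands. DOR is a descriptive secondary summary with no test attached. With a true response rate of 10% the trial stops at stage I with probability 0.62, with at most one response and no useful DOR curve. The point matters only if a responder dies without progression.

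A reader might go further and infer that Table 2 always gives a longer DOR. The 0.444 against 0.50 example shows that it does not, and the affected subject's own listed DOR is shorter under Table 2, since it ends at the last scan. Nor can a definite shift in the median be claimed. In the six-responder example the curve sits at exactly 0.50 at the third end date, so the reported median depends on the convention used there. The documents give no rates of progression or death among responders from which a percentage change could be derived.

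Simply adding a row that scores every death as an Event would create a new inconsistency. Table 3 censors deaths that follow new anticancer therapy or two missed assessments, so the same death could be an Event in DOR and a Censor in PFS.

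**Conclusion.** The inconsistency is real and is not resolved anywhere in the protocol or SAP. Programmed from Table 2, DOR would treat deaths without progression as uninformative censoring, which tends to lengthen the estimate without guaranteeing it in a small sample. With 4.6 to 8.9 responders expected once stage II opens, at true response rates of 10% and 25%, a single such death can change the Kaplan-Meier curve visibly. In the six-responder illustration the change at the third end date ranges from −0.06 to +0.17. With no such death the two rules give the same result.

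The textual finding rests on no assumption about hazards. The size is illustrative, because it rests on an assumed order of events. The documents do not support reading this as a threat to the primary result: the objective response rate and the Simon boundaries do not use DOR. The SAP should be corrected, but the design does not depend on it.

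**What to change.** State one rule in SAP 5.2.2 before database lock and apply it to all three DOR versions. Progression or death from any cause matches the formula, 6.11.1 and the PFS definition. To adopt it:

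- add death to the DOR definition and to the cut-off sentence;
- make the censoring sentence apply to subjects who have *neither progressed nor died*;
- add a Table 2 row, *Death without PD: date of death, Event*;
- carry over Table 3's censoring for new anticancer therapy and for two missed assessments, so that DOR and PFS treat the same death alike.

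If progression-only is intended, remove death from the formula and DOR from the death-date sentence in 6.11.1, and say explicitly that death without progression is censored.

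The cost is SAP wording, a few Table 2 rows and programming. Deaths are already recorded for PFS, so no new data are needed. The drawback of the first option is that reported DOR may be shorter than under Table 2.

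### The SAP's DOR rule lacks the PFS censoring for new anticancer therapy and for two missed assessments, so one responder's DOR can exceed his PFS

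*SAP*

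**What the plan says.** **DOR (SAP 5.2.2, Table 2).** There are two outcomes for a confirmed responder. "Disease progression documented per modified RECIST v1.1" is an event on the date of PD. Otherwise, "If a subject has not progressed, the subject will be censored at the date of last disease assessment", with the date of first response as the fallback. Neither the text nor the table mentions new anticancer therapy or missed assessments. The definition ends DOR at progression or at censoring, whichever comes first.

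**PFS (SAP 5.2.3, Table 3; repeated in substance in 6.4.2.3).** "Subjects who receive any further anticancer therapy for the disease before disease progression will be censored at the date of the last disease assessment" before that therapy began. Table 3 has a row for "Disease progression documented per modified RECIST v1.1 after new ACT", and its outcome is censoring. "If progression or death occurs after missing 2 scheduled disease assessments", the subject is censored at the last assessment. Two assessments count as missed when the gap exceeds 105 days in the first 24 weeks, or 210 days in follow-up.

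**Data cut-off.** The two sentences differ in the same way. For DOR: "To apply the cut-off date to DOR is to exclude disease assessments after cut-off date in the analysis". For PFS: "To apply the cut-off date to PFS is to exclude disease assessments, death and anti-cancer therapy date after cut-off date in the analysis". The anticancer therapy date is an input to PFS only.

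**Elsewhere.** Protocol 7.4.2.2 and SAP 6.4.2.2 add only that DOR is summarised by Kaplan-Meier. Protocol 7.4.2.3 promises a fuller censoring algorithm in the SAP, but for PFS. SAP 6.11.1 deals with imputing death dates and adds no censoring rule.

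**The concern.** Response starts after the first dose. If PFS and DOR share an end date, DOR must be shorter than PFS in the same subject. Different end-date rules remove that guarantee. A PD that the SAP regards as uninformative for PFS, because it follows another therapy or a long period without assessment, is taken at face value for DOR. In the new-therapy case the counted duration includes time under the next treatment. In the missed-assessment case it includes a stretch in which nobody knows whether the response continued.

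Section 5.2.2 also looks incomplete on its own terms. It takes the earlier of progression and censoring, but the only censoring it defines is for subjects who have not progressed. Under Table 2 the two dates never compete, so that clause has no effect. It would have one only if censoring could precede a PD, as in Table 3.

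At stake is how DOR can be read beside PFS, in a small group. The success boundary is 6 responses, and 8.5 are expected at an ORR of 25% in 34 subjects (0.25 × 34).

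**Working it through.** **1. The plan's own figures.** SAP 5.2.3 sets the gap limits at 2.5 times the assessment interval: 2.5 × 42 = 105 days and 2.5 × 84 = 210 days. Both reproduce. Neither limit appears in the DOR rule.

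**2. Formulas (SAP 5.2.2 and 5.2.3).**
- PFS = end date − first dose date + 1
- DOR = end date − date of first CR/PR that is later confirmed + 1

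First dose is day 1, and week w is day 7w + 1. The subjects below are hypothetical.

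**3. Missed assessments, no new therapy.** PR at week 6 (day 43), confirmed; last scan at week 24 (day 169); weeks 36 and 48 missed; PD at week 60 (day 421).
- Gap: 421 − 169 = 252 days, over the 210-day limit.
- PFS, Table 3: censored at 169 − 1 + 1 = **169 days**.
- DOR, Table 2: event at 421 − 43 + 1 = **379 days**.
- DOR with the PFS rule: censored at 169 − 43 + 1 = 127 days.

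**4. New therapy, no missed-assessment gap.** PR at week 6 (day 43), confirmed at week 12 (day 85); new therapy after week 12; PD recorded at week 24 (day 169).
- Gap: 169 − 85 = 84 days, under 105, so only the therapy rule applies.
- PFS, Table 3: censored at 85 − 1 + 1 = **85 days**.
- DOR, Table 2: event at 169 − 43 + 1 = **127 days**.
- DOR with the PFS rule: censored at 85 − 43 + 1 = 43 days.
- If nothing is recorded after week 12, Table 2 also censors at day 85, and the two endpoints share an end date.

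**5. Direction of the effect on Kaplan-Meier.** Assume six responders, five with DOR events at 85, 169, 211, 253 and 295 days.
- Sixth responder from step 4. As written (event at 127), S(169) = 3/6 = 0.50. With the PFS rule (censored at 43), S(169) = 4/5 × 3/4 = 0.60. The estimate **rises**.
- Sixth responder from step 3. As written (event at 379), S(211) = 3/6 = 0.50. With the PFS rule (censored at 127), S(211) = 5/6 × 3/4 × 2/3 = 0.417. The estimate **falls**.

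**6. Primary test.** For the design with 1/13 then 5/34 as the upper limits for no claim, the probability of rejection is the sum over x = 2 to 13 of P(X₁ = x) × P(X₂ ≥ 6 − x), where X₁ ~ Bin(13, p) and X₂ ~ Bin(21, p). It is 0.0957 at p = 0.10 and 0.811 at p = 0.25, in line with the stated 10% and 80%. DOR does not enter this calculation.

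**The case against.** The strongest reply is that the schedule largely closes off the new-therapy case. Imaging and marker draws stop when other systemic anticancer treatment starts (Protocol 5.3.1.1 and 5.3.1.3), and the post-treatment follow-up list in Protocol 2.2.1 ends at another anticancer treatment. A responder who moves to systemic therapy without PD normally has no later assessment, and Tables 2 and 3 then agree. This stands as a limit on frequency. It does not close the gap. The imaging stop in 5.3.1.1 and the note in Protocol 6.1 refer to systemic treatment, whereas the PFS rule covers any further anticancer therapy. A non-systemic treatment or an off-schedule assessment can therefore leave a recorded PD. Table 3 itself provides for one.

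The missed-assessment case is untouched by this reply. Treatment is capped at 12 cycles of 14 days (24 weeks), so durable responders are followed off drug at 12-week intervals. Protocol section 13 and SAP 6.8 both anticipate disruption from COVID-19.

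A second reply is that counting every PD whatever happened before it is a recognised strategy, and that the protocol promised a detailed algorithm for PFS only. That is fair: the SAP breaches nothing. But it neither states nor justifies a different strategy for DOR, and the idle clause in 5.2.2 points to an omission.

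A reader might go further and infer that the rule inflates DOR in the drug's favour. Step 5 of the working shows why that does not follow: aligning the rules replaces an event with an earlier censored time, which can raise or lower the curve.

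**Conclusion.** The inconsistency is real and explicit in the text. As written, DOR can exceed PFS in the same responder: 379 against 169 days in the missed-assessment example, 127 against 85 days in the new-therapy example. These are constructed cases. The documents give no basis for estimating how often either occurs.

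Three stronger readings are not supported.
- DOR will not generally run into the next treatment. Only the new-therapy case does that, and it should be uncommon.
- One subject is 1/8.5 = 11.8% to 1/6 = 16.7% of the responders at the counts given above. That is a share of the sample, not the size of a bias.
- The documents do not give DOR a leading supportive role. It is one of several secondary endpoints, summarised without a hypothesis test.

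ORR, the futility rule, type I error and power are unaffected. The point is worth correcting because so few subjects would contribute and the remedy is specific and cheap. How death enters DOR (the formula lists "Date of documented PD, death, or censoring", but Table 2 has no death row) is a separate question, not settled here.

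**What to change.** In SAP 5.2.2 and Table 2:
- For new anticancer therapy before PD, censor at the last evaluable assessment before the therapy started.
- For PD after two missed scheduled assessments (same 105- and 210-day limits), censor at the last evaluable assessment before the gap.
- In either case, use the date of first CR/PR if there is no later evaluable assessment.
- Add the anticancer therapy date to the DOR cut-off sentence.
- Apply the same rows to the RECIST-alone and marker-alone DOR.

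The clause taking the earlier of progression and censoring then has a meaning. DOR counting every PD regardless of these events can be kept as a sensitivity analysis.

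The cost is two table rows and one amended sentence. The inputs are already derived for PFS, and new anticancer therapy is already summarised (SAP 6.2.4.5), so no new data are needed. The downside is more censored observations in a small DOR sample.
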